17.4.1 Conversion from in person to remote study visits

- a) Screening, baseline and follow-up visits, regardless of whether in person or remote, are to be carried out within established visit windows.

- b) When an in person visit is converted to a remote visit, this may be carried out using a formal telemed or video conference system or by simple phone contact between the study staff and the study patient.
 - Regardless of the mechanism employed, the remote visit encounter must be accompanied by appropriate source documentation.
 - Study records should indicate when an in person visit is converted to a remote visit.
 - Study records should indicate whenever specific components of a study visit cannot be completed remotely due to the activation of the emergency protocol.
- c) Pre-specified phone follow-up visits are to continue as indicated in Section 7.2.3.3.

17.4.2 Components of study visits that can be carried out remotely

- a) Patient history or interim history.
 - Proceed using telemed, video or phone visits
- b) Review of concomitant medications
 - Proceed using telemed, video or phone visits
- c) Assessment of adverse events
 - Proceed using telemed, video or phone visits
- d) Modified study drug reconciliation
 - Proceed using telemed, video or phone visits
 - Review patient drug diary in detail and have patient provide copy for record if possible
 - Have participant describe available medication supply
 - Direct pill counts will not be possible
- e) Toxicity monitoring and pregnancy testing utilizing available commercial laboratories
 - Arrange for participant to have complete blood count with differential and platelet count, comprehensive metabolic panel and pregnancy testing completed at any available clinical laboratory
 - Pregnancy test may be carried out by qualitative urine or blood test as available
 - All clinical lab results must be collected and retained as source documents
- f) Study drug dispensing
 - Once a remote visit has been carried out and toxicity monitoring reviewed and approved, study drug may be shipped to the participant as detailed in Section 17.2.3
- g) Patient reported outcomes (PROs)
 - Email or mail (with return envelope and postage) visit-specific questionnaires to participants to complete and follow-up with them within 7 days to assure that participants have completed and returned them.
 - If preferred by participant or coordinator, questionnaires may be administered over the phone with the coordinator asking questions verbatim and stating all potential choices before recording participant responses.
 - Note that the SHAQ VAS page cannot be completed by phone; either mail the DCC provided form to the participant or skip its administration.
- h) Modified Mahler Transitional Dyspnea Index
 - Complete the Mahler TDI, if required for the visit, by phone
- i) Physician and Patient Global Assessments
 - Proceed using telemed, video or phone visits

17.4.3 Components of study visits that cannot be carried out remotely

Components of study visits that require direct examination or on-site completion may not be available during an emergency due to limitations in institutional or patient access. These components cannot be carried out remotely (by telephone or video visits) and the inability to complete will require deviation from that described in Protocol Section 7.2, Study Schedule. Absence of the following test results for a remote visit should be so noted in the study record as due to “COVID-19 Restrictions” or other emergency situation to address this deviation. Missing assessments may be collected out of window or at next on-site study visit, if appropriate.

- a) Physical examination
- b) mRSS
- c) Pulmonary function tests (spirometry and DLCO).
- d) Thoracic HRCT
- e) Blood collection for Biological Specimen Repository

17.4.4 Completion of pulmonary function tests at a remote facility

Pulmonary function tests are an established standard of care test for patients with SSc-ILD and required at routine intervals to monitor patients for the state of their lung disease, inter-current illnesses and treatment failures that might warrant additional evaluation and/or management.

In the setting of prolonged restrictions on travel or institutional access, or when ongoing safety concerns limit the ability for participating study patients to complete these outcome assessments at their assigned clinical site, the Executive Committee may allow such testing to be completed at a remote facility. Testing at remote facilities should be carried out in accord with ATS standards and by Certified Pulmonary Function Technologists. All requests for remote PFTs must be reviewed and approved in advance by the Executive Committee. Testing will be carried out as a recommended standard-of-care clinical assessment and therefore completed at the discretion of the study participant after being informed of the indications and potential financial implications. Data generated from such assessments may be included as official study outcome measures if reviewed by the Pulmonary Function QA Core and determined to meet minimum quality and reproducibility requirements.

17.5 REVISED SITE MONITORING

On-site monitoring visits may not be possible during an emergency. The Data Coordinating Center will utilize remote monitoring with remote source data verification, as required, to maintain oversight of clinical sites as outlined in Protocol Section 9, CLINICAL MONITORING.

Given the potential impact of an emergency situation on institutional resources, study personnel and the capacity to schedule and travel to visits, the time windows for the completion of study visits (as detailed in Protocol Section 7) may be extended by up to 30 days at the discretion of the Executive Committee. Decisions regarding the length of extended visit windows will take into account issues such as availability/access for visits, patient safety monitoring, standard-of-care and the presence of adequate study drug reserves.

APPENDIX LIST

Version	Date	Description	Significant Revisions
1.0	04/25/17	App #A: Study Questionnaires	
1.1	07/2019	App #B: Drug Packaging Inserts	Pirfenidone (Esbriet) drug packaging insert updated

### 3 Abbreviations and Definitions

AE	Adverse Event
ACR	American College of Rheumatology
ADL	Activities of daily living
ALT	Alanine Aminotransferase
ANC	Absolute Neutrophil Count
ANCOVA	Analysis of Covariance
AST	Aspartate Aminotransferase
ATS	American Thoracic Society
AUC	Area under the curve
BID	Twice daily
BDI	Baseline Mahler Modified Dyspnea Index
BAL	Bronchoalveolar lavage
BUN	Blood Urea Nitrogen
CDC	Center for Disease Control
CFR	Code of Federal Regulations
CLIA	Clinical Laboratory Improvement Amendments
Cmax	Maximum concentration
CMP	Clinical monitoring plan
CMV	Cytomegalovirus
COVID-19	Coronavirus Disease 2019
Cr	Creatinine
CRF	Case Report Form
CRISS	Combined Response index in Systemic Sclerosis
CTCAE	Common Terminology Criteria for Adverse Events V4.03-2010
CYC	Cyclophosphamide
CYP	Cytochrome P450
DCC	Data Coordinating Center
DLCO	Single-Breath Diffusing Capacity of the Lung for Carbon Monoxide
DLCO-Hb-%	DLCO, adjusted for age, height, gender and hemoglobin
DMARD	Disease-modifying antirheumatic drug
DSMB	Data Safety Monitoring Board
ECG	Electrocardiogram
eCRF	Electronic Case Report Forms
ERS	European Respiratory Society
EULAR	European League Against Rheumatism
FEV1	Forced Expiratory Volume in the first second
FDA	Food and Drug Administration
FVC	Forced vital capacity
FVC-%	Forced vital capacity as a percentage of the age-, height-, gender- and race-adjusted predicted value
GERD	Gastroesophageal reflux disease
GCP	Good Clinical Practice
GOO	Ground glass opacification
GLP	Good Laboratory Practices

GMP	Good Manufacturing Practices
H&P	History and physical
HBV	Hepatitis B virus
HCV	Hepatitis C virus
Hgb	Hemoglobin
HIPAA	Health Insurance Portability and Accountability Act
HRCT	High resolution computerized tomography
HRCT-TLC	HRCT-measured total lung capacity at maximum inspiration
HRQoL	Health-related quality of life
IB	Investigator's Brochure
IFN- $\gamma$	Interferon-gamma
ILD	Interstitial lung disease
IND	Investigational New Drug Application
IPF	Idiopathic pulmonary fibrosis
IRB	Investigational Review Board
JC	Polyomavirus JC
LCQ	Leicester Cough Questionnaire
LFTs	Liver function test
MCP-1	Macrophage chemotactic protein-1
MCTM	Markov Chain Transition Matrix
MITT	Modified intention to treat
MPA	Mycophenolic acid
MPAG	phenolic glucuronide metabolite of MPA
MMF	Mycophenolate mofetil; same as CellCept
MMP	Matrix metalloproteinase
MOP	Manual of Procedures
mRSS	Modified Rodnan Skin Score
NIH	National Institutes of Health
NSIP	Non-specific interstitial pneumonia
OHRP	Office for Human Research Protections
PAH	Pulmonary arterial hypertension
PDGF	Platelet derived growth factor
PFD	Pirfenidone; same as Esbriet
PFT	Pulmonary function test
PI	Principal Investigator
Plac	Placebo
PML	Progressive multifocal leukoencephalopathy associated with JC virus
PP	Per protocol
PPI	Proton pump inhibitors
PRCA	Pure Red Cell Aplasia
PRO	Patient Reported Outcome
PROMIS-29	Patient-reported outcomes measurement information system 29-item health profile
PVAN	Polyomavirus associated nephropathy
QA	Quality Assurance
QC	Quality Control
QGG	Quantitative ground glass

QHC	Quantitative honeycomb change
QIA	Quantitative image analysis
QILD-LM	Quantitative interstitial lung disease score in the lobe of maximal involvement
QILD-WL	Quantitative interstitial lung disease score in the whole lung
QLF-LM	Quantitative lung fibrosis score in the lobe of maximal involvement
QLF-WL	Quantitative lung fibrosis score in the whole lung
SABER	Statistical Analysis of Biomedical and Educational Research Unit
SAE	Serious Adverse Event
SAP	Statistical Analysis Plan
SGRQ	St. George's Respiratory Questionnaire
SHAQ	Scleroderma Health Assessment Questionnaire
SLS	Scleroderma Lung Study
SMC	Safety Monitoring Committee
SOC	System Organ Class
SOP	Standard Operating Procedure
SSc	Scleroderma (same as Systemic Sclerosis)
SSc-lc	Scleroderma with limited cutaneous features
SSc-dc	Scleroderma with diffuse cutaneous features
SSc-ILD	Scleroderma-related interstitial lung disease
TDI	Transitional Mahler Modified Dyspnea Index
TEAE	Treatment-emergent adverse event
TGF- $\beta$ 1	Transforming growth factor beta-1
TID	Three times daily
UCLA SCTC GIT 2.0	University of California, Los Angeles, Scleroderma Clinical Trials Consortium Gastrointestinal Scale
UIP	Usual interstitial pneumonia
ULN	Upper limit of normal
UP	Unanticipated Problem
US	United States
WBC	White blood cell

## 4 Introduction

### 4.1 Preface

This Statistical Analysis Plan (SAP) describes statistical methods and analyses for the SLS III (Scleroderma Lung Study III) trial. This document should be read in tandem with the SLS III Study Protocol version 2.5, dated November 17, 2021.

Scleroderma Lung Study III proposes to investigate a new combination therapy for patients with SSc-ILD that will combine the established effects of immunosuppression, as mediated by MMF, with the anti-fibrotic effects of PFD. The primary hypothesis is that the rapid onset and anti-fibrotic activity of PFD, which have been observed in the treatment of IPF, will complement the delayed anti-inflammatory and immunosuppressive effects of MMF, to produce a significantly more rapid and/or greater improvement in lung function over time than occurs in patients receiving control therapy with MMF (and Plac) alone. A secondary objective is to demonstrate that combination therapy with PFD and MMF is well tolerated, in comparison to MMF alone, and not associated with limiting toxicity that impacts on the overall treatment effect.

The SLS III study is designed as a Phase II multi-center, double-blind, parallel group, randomized and placebo-controlled clinical trial addressing the treatment of patients with active and symptomatic SSc-ILD. Participants were randomized in a 1:1 assignment to receive either oral MMF and Plac (acting as a control arm) or a combination of oral MMF and oral PFD (acting as an experimental arm), with both regimens administered for 18 months. The length of therapy, 18 months, was established based on prior studies with immunosuppressive therapy alone, which demonstrated that 18 months represents the time required to achieve a peak treatment response. The primary outcome will include physiologic measures of lung function, HRCT imaging measures of lung inflammatory and fibrotic changes, dyspnea, assessments of skin inflammation and thickening, and patient reported measures of symptoms and quality of life. Tolerability and toxicity of the two treatments will also be assessed.

### 4.2 Scope of the Analyses

The purpose of this document is to describe primary, secondary and exploratory statistical analyses to be conducted with regard to the SLS III clinical trial. Ancillary analyses are not covered in this document.

## 5 Study Objectives and Endpoints

### 5.1 Study Objectives

#### 5.1.1 Primary Objective

To assess the impact of combined PFD and MMF, as compared to treatment with MMF alone (i.e., combined with placebo), on the overall course of lung function over an 18-month course of therapy.

#### 5.1.2 Secondary Objective

To demonstrate that combination therapy with PFD and MMF is well tolerated, in comparison to MMF alone, and not associated with limiting toxicity that impacts on the overall treatment effect.

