3 STUDY OBJECTIVES AND PURPOSE

The primary purpose for this Phase II clinical investigation is to determine the relative efficacy and safety of combining two drugs with different mechanisms of action, PFD and MMF, for the treatment of Scleroderma-related ILD.

It is hypothesized that the rapid onset and anti-fibrotic activity of PFD, which have been observed in the treatment of IPF, will complement the delayed anti-inflammatory and immunosuppressive effects of MMF, to produce a significantly more rapid and/or greater improvement in lung function over time than occurs in patients receiving control therapy with MMF and Plac.

The Primary Objective is therefore to assess the impact of combined PFD and MMF, as compared to treatment with MMF alone (i.e combined with Plac), on the overall course of lung function over an 18-month course of therapy.

A secondary objective is to demonstrate that combination therapy with PFD and MMF is well tolerated, in comparison to MMF alone, and not associated with limiting toxicity that impacts on the overall treatment effect.

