  - a. Using 4 points increments: worsen (1 to 4,  $\geq 5$ ), no change (=0), improved ( $\leq -13, -12$  to -9, -8 to -5, -4 to -1).
  - b. Improved (< -5), no change (-5 to 5), and decreased (> 5).
9. The proportion of participants in each treatment arm achieving the TDI focal score at month 18 as :
  - a. Improved by 1-3, 4-6 and 7-9 points, no change (0) and worsened by 1-3, 4-6 and 7-9 points.
  - b. Improved (>0), no change, deterioration (<0).
10. Tolerability and toxicity of combined MMF and Plac vs MMF and PFD over the course of the 18-month treatment period.
  - a. The time from start of treatment to withdrawal or removal from active drug therapy for any reason.
  - b. Number of participants with treatment-emergent adverse events related to study medication as assessed by system organ classification using preferred Medical Dictionary for Regulatory Activities (MedDRA) terms.

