## 8.6 Multiple Testing

Statistical testing is conducted at the 0.05 significance level using two-tailed tests; two-sided p-values are reported. No adjustments for multiplicity were planned since there is one primary analysis of the primary endpoint at the end of the study. Secondary analyses of the primary endpoint and analyses of the secondary endpoints serve to assess the robustness of the results and consistency of treatment effect on clinical outcomes important in this disease.

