### 9.4 Treatment Compliance

Compliance with study medication (MMF and PFD/Plac) is assessed and summarized, including

- the proportion of participants who adhered to study treatment, overall and at each study visit,
- the median duration of adherence to study treatment (defined in section 11.1),
- the proportion of participants reaching maximum dose,
- the proportion of participants who sustain their maximum dose,
- the time to reach the maximum dose, and
- the time remaining at the maximum dose.

These are calculated and summarized overall and by treatment group. The maximum dose is 12 pills/day for MMF (1500 mg) and 9 pills/day for PFD (801 mg)/Plac. The proportion of the maximum dose that the participants reached during study period is summarized overall and by treatment group. Participants were expected to take study medication unless it was permanently discontinued due to an AE. The study medication log (Form 027), adverse event form (Form 044), serious adverse event form (Form 045) and final status form (Form 035) are used to derive the compliance measure.

The proportion of participants who permanently discontinued study medication will be summarized with descriptive statistics, overall and by treatment group. A Kaplan-Meier curve will present the time to permanent discontinuation of study medication by treatment group. A listing of these participants with their reason for permanent discontinuation of study medication will be provided.

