## 11 Safety Analyses

Safety data, including AEs, clinical laboratory tests, vital signs, physical examinations, and concomitant medication usage will be summarized descriptively overall and by treatment group for the Safety Population. AEs include frequency of events and/or incidence of study subjects experiencing events, by study arm for the following:

- a) Study-defined treatment failures
- b) Study-defined treatment emergent AEs of special Interest
- c) All treatment-emergent AEs, total and by organ system classification
- d) All treatment-emergent AEs related to study medication, total and by organ system classification
- e) All treatment-emergent SAEs, total and by organ system classification
- f) All treatment-emergent SAEs related to study medication, total and by organ system classification
- g) All treatment-emergent AEs and SAEs that result in discontinuation of study medication
- h) Time to treatment failure
- i) Time to treatment-emergent AEs and SAEs resulting in premature discontinuation of study medication

For categorical safety outcomes, numbers and percentages will be used. For continuous safety outcomes, number, mean, standard deviation, median, interquartile range, minimum and maximum are used to summarize changes from baseline to each study visit in laboratory tests and vital signs. Percent change from baseline for laboratory values are summarized. The primary organ system associated with each adverse event was coded by the medical monitor. Kaplan-Meier methods are used to summarize graphically the time to treatment failure, and treatment-emergent AEs and SAEs that result in premature discontinuation of study medication.

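### The plan sets out to demonstrate comparative tolerability but reports only counts, percentages and Kaplan-Meier plots, with no between-arm estimate, interval or margin

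*SAP*

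**What the plan says.** Protocol Section 3 states the aim as follows: "A secondary objective is to demonstrate that combination therapy with PFD and MMF is well tolerated, in comparison to MMF alone". SAP 5.1.2 repeats it: "To demonstrate that combination therapy with PFD and MMF is well tolerated, in comparison to MMF alone, and not associated with limiting toxicity".

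SAP 5.2.2 item 10 names two endpoints for it:

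- 10a: "The time from start of treatment to withdrawal or removal from active drug therapy for any reason".
- 10b: "Number of participants with treatment-emergent adverse events related to study medication as assessed by system organ classification".

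The planned analyses are:

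- SAP 11, categorical outcomes: "For categorical safety outcomes, numbers and percentages will be used".
- SAP 11, time-to-event outcomes: "Kaplan-Meier methods are used to summarize graphically the time to treatment failure", and likewise for adverse events leading to discontinuation.
- SAP 9.4, drug discontinuation: "A Kaplan-Meier curve will present the time to permanent discontinuation of study medication by treatment group", with descriptive statistics and a listing of reasons.

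SAP 8.6 gives the general testing rule: "Statistical testing is conducted at the 0.05 significance level using two-tailed tests". No test, between-arm estimate, interval or margin is attached to a tolerability or toxicity outcome. By contrast, the SAP plans 95% intervals for the primary treatment difference (10.1), medians with intervals and a stratified log-rank test for time to FVC-% response (10.2.2 item 5), and an odds ratio with an interval for FVC-% improvement (10.2.2 item 6).

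**The concern.** A claim that one regimen is well tolerated compared with another concerns the size of a difference. Percentages side by side and two survival curves show the observed difference. They do not show which true differences the data leave open. With few participants that range is wide, and similar-looking arms are weak evidence of similar tolerability.

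SAP 14 removes or simplifies several efficacy and exploratory analyses because enrolment stopped early, but the verb in SAP 5.1.2 is unchanged. At stake is a report that this objective was met while the data remain compatible with a sizeable excess of drug discontinuation.

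**Working it through.** The documents give no power or precision figure for tolerability; the power tables in SAP 7 concern FVC-% only. There is therefore no stated figure to reproduce.

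**Inputs**

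- 51 participants indexed in the primary model (SAP 10.1); 75 per arm planned (SAP 7).
- Discontinuation for an adverse event: 14.6% on pirfenidone, 9.6% on placebo (Protocol 2.3.1.2.4).
- Gastrointestinal dose reduction or interruption: 18.5% against 5.8% (Protocol 2.3.1.2.3).
- Nausea: 36% against 16% (Protocol Table 2.3.1.2.4a).
- Assumptions: the Safety Population is close to 51 and splits 25/26 or 26/25, and the IPF rates apply to patients taking MMF.

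**Step 1: what the raw percentages would show.** Let X and Y be independent binomial counts in the pirfenidone and placebo arms. Sum P(X=i)·P(Y=j) over all outcomes that meet each condition. The two figures at 51 participants are for the two possible splits.

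| Outcome | Size | Difference ≤5 points | Any excess on pirfenidone |
|---|---|---|---|
| AE discontinuation | 51 | 52-56% | 65-76% |
| AE discontinuation | 75/75 | 48% | 79% |
| GI dose change | 51 | 21-24% | 90-95% |
| Nausea | 51 | 10-12% | 94-96% |

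The true difference for AE discontinuation is itself 5 points, so about half of trials falling at or below 5 is expected. More telling is that 24-35% of trials (100% minus 65-76%) would show no excess at all.

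**Step 2: what near-equal counts leave open.** Take 4/26 against 4/25 and the Newcombe interval built from Wilson limits.

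- Rates: 15.4% (Wilson 6.15% to 33.53%) and 16.0% (Wilson 6.40% to 34.65%); difference -0.6 points.
- Lower limit: -0.0062 - √[(0.1538-0.0615)² + (0.3465-0.1600)²] = -0.0062 - 0.2081 = -0.214.
- Upper limit: -0.0062 + √[(0.3353-0.1538)² + (0.1600-0.0640)²] = -0.0062 + 0.2053 = +0.199.

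The interval is about -21 to +20 points, so an excess about four times the documented 5 points is not excluded. At the planned size, 7/75 in each arm gives ±9.9 points, which still includes 5.

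**Step 3: could a margin rescue the word?** The documents give none, so a range is shown. With both arms truly at 9.6%, one-sided 2.5% and 80% power, n per arm = (1.96+0.84)²·2·0.096·0.904/δ². This gives 545, 137, 61 and 35 per arm for δ of 5, 10, 15 and 20 points. At about 25.5 per arm, the chances of meeting those margins are 9%, 23%, 44% and 68%.

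**The case against.** The plan offers more than counts. Endpoint 10a is a time-to-event measure that fits tolerability well. SAP 9.4 adds discontinuation curves by arm, reasons, adherence and time at maximum dose. The objective is also qualified: it concerns limiting toxicity that affects the overall treatment effect. The per-protocol analysis and the FVC-% summaries by timing of discontinuation (SAP 10.2.1 items 1 and 6) address that part. Descriptive safety reporting is usual in Phase II. The table shells are in a separate document that is not available here, and the Safety Population may exceed 51 because it requires no post-baseline efficacy assessment.

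All of this stands, but it leaves the gap open. The curves are graphical, with no planned hazard ratio or interval, and the FVC-% analyses do not estimate how much tolerability differs between arms. The provision in Protocol 10.4.7.1 for the DSMB to request inferential testing concerns monitoring, not the final report.

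A reader might go further and infer that a real excess of the documented size would usually look like no difference, or that non-significance will be read as tolerability. The documents support neither. No safety test is planned, and nothing says a non-significant result will be taken as tolerability. In the plain percentages, the nausea and gastrointestinal dose-change excesses would lean against pirfenidone in at least 90% of trials.

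**Conclusion.** The point holds as a mismatch between objective and analysis. A comparative demonstration is promised, and no planned output puts a limit on the difference between arms. The practical weight falls on outcomes with modest excesses, above all AE discontinuation, which is the documented figure closest to limiting toxicity. There the observed difference would often look small or absent, and near-equal counts leave roughly ±20 points open. Those figures depend on the assumed Safety Population size, the 25/26 split and the transfer of IPF rates. The mismatch itself depends on none of them. The primary endpoint is unaffected.

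**What to change.** 1. In SAP 9.4 and 11, for the Safety Population, report the MMF+PFD minus MMF+Plac risk difference with a two-sided 95% score or exact interval for permanent discontinuation of study drug due to an adverse event, any related treatment-emergent adverse event (10b), any serious adverse event, and any adverse event of special interest.
2. Report a hazard ratio with a 95% interval for time to withdrawal or removal from drug (10a).
3. State that conclusions on tolerability rest on these intervals, and that the absence of an apparent difference will not be reported as showing comparable tolerability.
4. In SAP 5.1.2, change the objective to: *to estimate the tolerability and toxicity of PFD plus MMF relative to MMF plus placebo*. If the stronger verb is kept, a justified margin is needed, and the sizes above show that a tight one is out of reach.

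The cost is SAP wording, four interval estimates from events already tabulated, and one model, with no new data or participants. The change should be made before unblinding. The price is a less favourable claim, because the intervals will be wide. For example, if the 24% attrition assumed in SAP 7 were taken as a rough guide to drug withdrawal, there would be about 0.24 × 51 ≈ 12 events. The 95% limits would then lie a factor of about exp(1.96 × 2/√12) ≈ 3.1 either side of the hazard ratio.
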